4.3.3. Secondary Safety

The analyses will be based on the Exposed Set.

The safety follow-up time will be tabulated by group using descriptive statistics (mean, median, minimum, maximum).

4.3.3.1. Solicited events (Chinese participants only)

- For solicited events during the 7-day follow-up period (i.e., the day of study intervention administration and 6 subsequent days) after vaccination, the following summaries will be provided by group: Compliance in completing solicited events information will be tabulated:
 - Number and percentage of participants with solicited events occurrence status data will be tabulated with exact 95% CI.
- Number and percentage of participants reporting below each individual event will be tabulated with exact 95% CI, for any grade, grade 3 and resulting in medically attended visit:
 - any solicited administration site event
 - any solicited systemic event
 - any solicited event
 - each individual administration site event
 - each individual systemic event
- The percentage of participants with each solicited administration site event and solicited systemic event (any grade and grade 3) will be represented graphically.
- For fever, the number and percentage of participants reporting fever by half degree (°C) cumulative increments during the 7-day follow-up period after vaccination will be tabulated as per GSK grading scale and China grading scale.
- The duration in days of each individual solicited events will be tabulated using descriptive statistics (mean, min, Q1, median, Q3, maximum). The same computations will be done for the number of days with Grade 3 solicited events.

4.3.3.2. Unsolicited adverse events (Chinese participants only)

The verbatim reports of unsolicited AEs, including SAE and AESI (i.e. pIMDs and AF), will be coded according to the MedDRA Dictionary for Adverse Reaction Terminology. The unsolicited AEs will be reported using MedDRA Primary System Organ Class (SOC), High Level Term (HLT) and Preferred Term (PT), unless otherwise specified.

The unsolicited AEs during the 30-day follow-up period (i.e., the day of study intervention administration and 29 subsequent days) after the study intervention, including SAEs and AESIs (i.e. pIMDs and AF), will be summarized by group as:

- Number and percentage of participants reporting each below type event with exact 95% CI, for all events and for non-serious events:
 - unsolicited AEs
 - grade 3 unsolicited AEs
 - causally related unsolicited AEs
 - grade 3 causally related unsolicited AEs
 - unsolicited AEs resulting in a medically attended visit
- Number and percentage of participants reporting each below type event will summarized with exact 95% CI:
 - unsolicited AEs reported within 30 minutes following vaccination
 - grade 3 unsolicited AEs reported within 30 minutes following vaccination

4.3.3.3. Pooling analysis of solicited and unsolicited AEs (Chinese participants only)

Solicited events and unsolicited events, including SAE and AESI (i.e. pIMDs and AF), will be pooled and summarized by group as:

- Number and percentage of participants reporting each below type event with exact 95% CI, for events during the 7-day and for events during the 30-day follow-up period after the study intervention, and for any grade, grade 3, grade 3 non-serious AE, and AEs resulting in a medically attended visit:
 - any solicited administration site event
 - any solicited systemic event
 - any AE
- For web posting purposes, the number of occurrences and the number and percentage of participants with non-serious AEs (solicited and unsolicited combined, also including pIMD) during the 30-day follow-up period will be produced by SOC and PT.

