**10.3.4. Unsolicited AE**

 
• Definition of unsolicited AE
 

 
• An unsolicited AE is an AE that was either not included in the list of solicited events or could be included in the list of solicited events but with an onset outside the specified period of follow-up for solicited events. Unsolicited AEs must have been communicated by participants who has signed the informed consent. Unsolicited AEs include both serious and nonserious AEs.
 
• Potential unsolicited AEs may be medically attended (i.e., symptoms or illnesses requiring a hospitalization, emergency room visit, or visit to/by a healthcare provider). The participants will be instructed to contact the site as soon as possible to report medically attended event(s), as well as any events that, though not medically attended, are of participant concern. Detailed information about reported unsolicited AEs will be collected by qualified site personnel and documented in the participant's records.
 
• Unsolicited AEs that are not medically attended nor perceived as a concern by the participant will be collected during an interview with the participants and by review of available medical records at the next visit.
 

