6.3.4. Reporting period of adverse events

Safety data	Collected from	Reporting period for analysis
Solicited events	Chinese participants	Within 7 days following the vaccination, i.e. Day 1-7
Unsolicited solicited events	Chinese participants	Within 30 days following the vaccination, i.e. Day 1-30
SAEs, pIMDs	Chinese participants	6 months after vaccination, i.e. Day 1-183
	Overseas participants	
 Up to study end (Month 6) 6 months after vaccination, i.e. Day 1-183
SAEs related to study intervention, pIMDs related to study intervention, fatal SAEs, AE/SAE leading to withdrawal from study	Chinese participants	
 Up to study end (Month 6 or last ARI visit, whichever is later) 6 months after vaccination, i.e. Day 1-183
	Overseas participants	
 Up to study end (Month 6) 6 months after vaccination, i.e. Day 1-183

Atrial fibrillation (AF) reported as AE or SAE would follow the reporting period of unsolicited AE or SAE, respectively.

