6.3.7. Pooling of solicited and unsolicited adverse events

Unsolicited adverse events with missing administration site flag will be considered systemic.

Solicited events will be coded by MedDRA as per the following codes:

Solicited event	Lower level term code	Corresponding Lower level term decode
Pain	10022086	Injection site pain
Redness (Erythema)	10022061	Injection site erythema
Swelling	10053425	Injection site swelling
Fever	10016558	Fever
Headache	10019211	Headache
Fatigue	10016256	Fatigue
Myalgia	10028411	Myalgia
Arthralgia	10003239	Arthralgia

Note that these codes might be adapted depending on the current version of MedDRA at the time of analysis.

Multiple events with the same preferred term which start on the same day are counted as only one occurrence.

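### Two of the three rows in the SAP's pooled solicited-plus-unsolicited table are restricted to solicited events, so they pool nothing and their any-grade 30-day counts equal their 7-day counts

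*SAP*

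**What the plan says.** The lead sentence of SAP 4.3.3.3 reads: "Solicited events and unsolicited events, including SAE and AESI (i.e. pIMDs and AF), will be pooled and summarized by group as". The summary is given "for events during the 7-day and for events during the 30-day follow-up period after the study intervention", each with columns for any grade, grade 3, grade 3 non-serious and medically attended events. The three rows are "any solicited administration site event", "any solicited systemic event" and any AE.

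SAP 6.3.4 sets the reporting period for solicited events as "Within 7 days following the vaccination, i.e. Day 1-7" and for unsolicited events as "Within 30 days following the vaccination, i.e. Day 1-30". Under protocol 10.3.4, an unsolicited AE includes one that "could be included in the list of solicited events but with an onset outside the specified period of follow-up for solicited events".

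SAP 6.3.7, the derivation section for this pooling, adds: "Unsolicited adverse events with missing administration site flag will be considered systemic".

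**The concern.** The section's title and lead sentence describe a pooled analysis, but two of its row labels exclude everything unsolicited. A programmer who follows the labels gets a solicited-only percentage under a 30-day heading. A programmer who follows the lead sentence and SAP 6.3.7 counts unsolicited site and systemic AEs as well, and can only get an equal or larger number. A pre-specified plan should not allow both.

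At stake are the total local and total systemic event percentages per China group, which no other planned table gives. Under the literal reading, an injection-site reaction that starts after Day 7, or an unsolicited systemic AE on any day from 1 to 30, is missing from its own site or systemic total.

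**Working it through.** The plan states no figure for this table, so there is nothing to reproduce. The check compares definitions, followed by a counting illustration.

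**1. Can a solicited event start on Days 8 to 30?** No. SAP 6.3.4 limits solicited events to Days 1 to 7, and protocol 10.3.4 makes a listed event with later onset an unsolicited AE.

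**2. What do the two rows contain at 7 days?** Only solicited events from Days 1 to 7. SAP 4.3.3.1 already tabulates the same two labels over the same window for any grade, grade 3 and medically attended events. The only addition is the grade 3 non-serious column. Unsolicited events from Days 1 to 7 are absent.

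**3. What do they contain at 30 days?**
- Any grade: a participant counts if at least one solicited event occurred. All such events start by Day 7, so the 30-day count equals the 7-day count.
- Grade 3 and medically attended: equality is not guaranteed. SAP 6.3.5.2 lets a solicited event end after the solicited period and allows for a maximum intensity of 3 recorded while it is ongoing. An event that starts on Day 6 could reach grade 3, or lead to a visit, on Day 10.
- Unsolicited events: none, in any column.

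**4. Does the SAP show what was meant?** SAP 6.3.7 sorts unsolicited AEs into site or systemic. SAP 4.3.3.2 does not use that split, and the web-posting table in 4.3.3.3 is by SOC and PT. If the two pooled rows exclude unsolicited AEs, the rule has no evident use.

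**5. Where do Day 8 to 30 events still appear?** In the 30-day any-AE row of the same table, in the unsolicited AE summaries of SAP 4.3.3.2, and (if non-serious) in the 30-day SOC/PT table.

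**6. Illustration.** The planned vaccine group in China is 1800 × 2/3 = 1200. The rates below are assumptions, not from the documents, and are taken as independent. For one row, suppose 60% have a solicited event, 5% an unsolicited event of the same class on Days 1 to 7, and a share *a* one starting on Days 8 to 30.

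- Literal row: 0.60 × 1200 = 720 in both windows.
- Pooled row, 7 days: 1 − 0.40 × 0.95 = 62.0%, or 744.
- Pooled row, 30 days: 1 − 0.40 × 0.95 × (1 − *a*).

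| *a* | Pooled 30-day | Participants | Literal row short by |
|---|---|---|---|
| 5% | 63.9% | 767 | 3.9 points |
| 10% | 65.8% | 790 | 5.8 points |
| 20% | 69.6% | 835 | 9.6 points |

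This shows only how the two readings diverge. It does not estimate the understatement in this trial.

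**The case against.** The strongest reply is that this is a label slip of little consequence. The row labels match those of SAP 4.3.3.1, which suggests copying, and the title and lead sentence make the intent visible. The stated safety endpoints are each solicited event within 7 days and unsolicited AEs within 30 days. SAP 4.3.3.1 and 4.3.3.2 serve both in full, and no pooled site or systemic total is an endpoint. SAP 6.3.7 may also be standard wording: a neighbouring section, 6.3.5.1, is written for studies with paper diaries in general. All of this stands as a limit on importance. It does not make the labels correct, because taken as written they still select the wrong events for a stated analysis.

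Three stronger readings are tempting but not supported.

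- A reader might infer that the whole 30-day table repeats the 7-day one and that late events vanish from the report. The any-AE row does not repeat, and late events remain in the outputs listed in step 5.
- A reader might note that 23 of the 30 days (77%) have no solicited collection and conclude that every column must be identical, or that 77% of events are lost. The first fails because solicited events can continue past Day 7. The second treats a share of the calendar as a share of events.
- A reader might infer bias between vaccine and placebo. The documents give no rate of late or unlisted reactions by group, so neither a direction nor a size can be claimed.

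**Conclusion.** The point holds for two rows of one table. As labelled, the site and systemic rows of SAP 4.3.3.3 pool nothing. They repeat SAP 4.3.3.1 at 7 days, show the same any-grade participants again at 30 days, and omit unsolicited site and systemic AEs from Days 1 to 30. This conflicts with the section's own lead sentence and leaves the site/systemic rule of SAP 6.3.7 without evident use.

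What is lost is the pooled site/systemic split for about 1200 vaccine and 600 placebo participants (1800 at 2:1), not the events themselves. The size of the understatement cannot be given from the documents. The any-grade equality rests on the onset definitions in SAP 6.3.4 and protocol 10.3.4; the intent to pool is inferred from the title, the lead sentence and SAP 6.3.7. The table is descriptive, so the correction should be made, but it does not touch the primary non-inferiority tests, alpha or sample size.

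**What to change.** In SAP 4.3.3.3, replace the two labels with *any administration site event (solicited or unsolicited)* and *any systemic event (solicited or unsolicited)*. Classify unsolicited AEs by the administration-site flag of SAP 6.3.7, for both the 7-day and the 30-day window. Keep the any-AE row, and leave solicited-only results in SAP 4.3.3.1.

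The cost is two row labels and their selection rule in the SAP and the table shell. No new data should be needed, provided the flag is on the eCRF. Its collection is inferred from SAP 6.3.7, because neither document describes it elsewhere, so confirm this before the change is made.

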4.3.3.4. SAEs, pIMDs and AEs leading to withdrawal from study

The following summarized will be provided by group:

- Number and percentage of participants reporting each below type event up to study end, with exact 95% CI:
 - any SAE (for overseas participants only)
 - any pIMD (for overseas participants only)
 - any SAE related to study intervention administration
 - any pIMD related to study intervention administration
 - any fatal SAE
- Number and percentage of participants reporting each below type event up to 6 months after vaccination, i.e. during Day 1-183, by the MedDRA Primary SOC, HLT and PT, with exact 95% CI:
 - SAE
 - pIMD
 - SAE related to study intervention administration
 - pIMD related to study intervention administration
 - fatal SAE
- All SAEs, pIMDs and AEs leading to withdrawal from study will also be described in detail in tabular listings.

4.3.3.5. Other adverse events

- For Chinese participants only:
 - Atrial Fibrillation (AF) AESIs will be described in a tabular listing including the characteristics of the AE (causality, maximum intensity), day to onset and outcome.
 - AF AESIs will be tabulated within the summary of AEs or SAEs according to their classification.

4.4. Tertiary/Exploratory Analyses

Not Applicable.

4.5. Other Safety Analyses

Not applicable.

4.6. Other Analyses

As per the local requirement, descriptive immunogenicity analysis will be performed for participants from Republic of Korea. Details refer to Humoral immune response in terms of RSV-A and RSV-B neutralizing antibody titres expressed as GMT and SRR will be calculated at baseline (GMT only), 1 month and 6 months after the RSVPreF3 OA investigational vaccine administration. The comparison between humoral antibody response at 1-month post-vaccination and historical antibody response collected from Korean participants in RSV OA=ADJ-006 study will be conducted descriptively.

4.7. Interim Analyses

4.7.1. Sequence of analyses

The analyses will be performed stepwise:

- **Day 31 (PCA) analysis:** The first analysis will be performed when immunogenicity and reactogenicity data up to Visit 2 (Day 31) are available. This analysis will be considered as final for those data. Safety data up to database lock point will also be included into the analysis. The analysis will be performed by study statistician who will be unblinded to the details of the treatment assignments at the time of the Day 31 analysis.
- **Month 6 Safety Analysis:** An optional analysis may be conducted when safety data up to Month 6 are available.
- **End of Study Analysis:** The final analysis will be performed when all data for the secondary endpoints of descriptive immunogenicity at Month 6, ARI surveillance and safety up to study conclusion are available.

4.8. Changes to Protocol Defined Analyses

A blinded safety analysis was conducted using data of 11Mar2025 to support the CDE consultation of RSV OA=ADJ-028 study.

There were no other changes or deviations to the originally planned statistical analysis specified in the protocol amendment 1 (Dated: 15 Feb 2024).

5. SAMPLE SIZE DETERMINATION

The target sample size for the study is approximately 2600 participants: i.e. 1800 participants in China [2:1 randomization allocation between RSV OA group (China) and Placebo group (China)], 800 participants in RSV OA group (Overseas).

The sample size in the groups receiving the investigational vaccine is driven by need to meet local regulatory requirements and the statistical power to prove the primary NI objectives.

Based on a sensitivity analysis for the study power (Table 7), the sample size is able to provide $\geq 90\%$ power to demonstrate the primary NI objectives in RSV OA group (China) compared to the RSV OA group (Overseas) for all the scenarios presented, assuming an attrition rate of 10%:

- The Power of the NI testing for the GMT is calculated by SAS 9.4 using the two-sample t-test for non-inferiority assuming equal variance.
- The Power of the NI testing for the SRR is calculated by SAS 9.4 using the non-inferiority tests for the difference between two proportions applying the method of Miettinen and Nurminen.

Table 7 Sensitivity analysis for the power of co-primary NI testing

	Statistical Assumptions				Individual Powers				Overall Power
Hypothesis	H1	H2	H3	H4	H1	H2	H3	H4	
Endpoint	GMR*	SRR**	GMR*	SRR**	GMR	SRR	GMR	SRR	
Scenario 1	1.06	80.3%, 82.3%	1.10	76.7%, 73.4%	100%	100%	100%	90.5%	90.5%
Scenario 2	1.11	80.3%, 83.2%	1.14	76.7%, 75.0%	100%	100%	100%	98.2%	98.2%
Scenario 3	1.17	80.3%, 84.5%	1.18	76.7%, 77.0%	99.9%	100%	99.8%	99.9%	99.6%
Scenario 4	1.17	81.7%, 83.2%	1.19	77.4%, 75.0%	99.9%	100%	99.6%	96.5%	96.0%

H1, H2, H3, H4 = Null hypothesis 1, 2, 3 and 4 respectively.

* GMR is the geometric mean titer ratio of RSV OA group (Overseas) / RSV OA group (China). Its individual level standard deviation of log10 titers for RSV neutralization is assumed as 0.45.

** The values are the assumed seroresponse rate in the RSV OA group (Overseas) and RSV OA group (China), respectively.

SRR = Seroresponse rate.

The assumptions are based on the data from RSV OA=ADJ-004 study.

Participants who withdraw from the study will not be replaced.

6. SUPPORTING DOCUMENTATION

6.1. Appendix 1 Study Population Analyses

Unless otherwise specified, the study population analyses will be based on the Exposed Set. A summary of the number of participants in each analysis set will be provided.

6.1.1. Participant Disposition

A summary of the number and percentage of participants screened, screen failures, those who completed the study as well as those who prematurely withdrew from the study will be provided. Reasons for screen failure and study withdrawal will be summarized. This analysis will be based on the Screened set, Enrolled set and Exposed Set.

6.1.2. Demographic and Baseline Characteristics

Below demographic will be summarized descriptively by group on the Exposed Set and Per-Protocol Set:

- Age at vaccination
 - age will be presented in years.
 - summarized as continuous and categorical (60-69, 70-79, ≥ 80 YOA)
- Sex
- Ethnicity
- Race
- Country
- Body Mass Index (BMI), which is auto-calculated by the eDC system.

Subgroup analyses will be performed by age categories (60-69, 70-79, ≥ 80 YOA) for the characteristics.

Below baseline characteristics will be summarized descriptively by group on the Exposed Set:

- Vital signs: height, weight, systolic blood pressure, diastolic blood pressure, heart rate, respiratory rate
- Smoking status
- Frailty status determined using the Gait speed test

The number and percentages of participants with medical history (including baseline comorbidities) classified by the MedDRA Primary SOC, HLT and PTs will be tabulated by group for the Exposed Set.

The number and percentages of participants with each comorbidity category will be summarized by group for the Exposed Set.

If the summary of demographics meets the criteria for de-identification, as described in the relevant procedural document, a de-identified version should be produced.

6.1.3. Protocol Deviations

Important protocol deviations will be summarized.

Protocol deviations will be tracked by the study team throughout the conduct of the study. These protocol deviations will be reviewed to identify those considered as important as follows:

- Data will be reviewed prior to the freezing the database to ensure all important deviations (where possible without knowing the study intervention details) are captured and categorised in the protocol deviations dataset.
- This dataset will be the basis for the summaries of important protocol deviations.

A summary of important protocol deviations will be provided by group based on the Screened Set and Enrolled Set.

The number of participants screened for the study as well as the number of participants excluded from the Enrolled set, Exposed Set and the Per-Protocol Set analyses will be tabulated. These will be based on the Screened set, Enrolled Set and the Exposed Set, respectively.

6.1.4. Concomitant Medications

Concomitant medications will be coded using the WHO Drug dictionary.

The number and percentage of participants starting any concomitant medication (any medication, any antipyretic, any antipyretic taken prophylactically and any antibiotic) during the 7-day and the 30-day follow-up period after the study intervention will be tabulated per study group with exact 95% CI for the Exposed Set.

6.1.5. Concomitant Vaccinations

The number and percentage of participants starting any concomitant vaccination during the 30-day follow-up period after the study intervention will be tabulated per study group with exact 95% CI for the Exposed Set.

6.2. Appendix 2 Electronic Clinical Outcome Assessment (eCOA) Compliance

Not applicable.

6.3. Appendix 3 Data Derivations Rule

6.3.1. Attributing events to vaccine doses

If an event starts on the same day as a study dose, the relative dose will be derived from the additional information provided in the eCRF using the contents of the flag indicating if the event occurred before or after study dose. If 'after study intervention' is selected, the relative dose for the event will be the one administered on the start day of the event. If 'before study intervention' is selected, the event will not be attributed to the study vaccination.

6.3.2. Handling of Partial Dates

When partially completed dates (i.e., dates missing a day and/or month) are used in calculations, the following standard rules will be applied:

- A missing day will be replaced by 15
- A missing day and month will be replaced by June 30th.

The following exceptions apply:

- Adverse events start dates with missing day:
 - If the month is not the same as the vaccine dose, then the imputed start date will be the 1st of the month.
 - If the event starts in the same month as the vaccine dose, the flag indicating if the event occurred before or after vaccination (AE.AESTRTPT) will be used to complete the date. If ‘after study intervention’ is selected, the imputed start date will match the vaccine dose given during that month. If ‘before vaccination’ is selected, the imputed date will be one day before the vaccine dose given during that month.
- Adverse events start dates with missing day and month:
 - If the year is not the same as the vaccine dose, then the imputed start date will be the 1st of January.
 - If the event starts in the same year as the vaccine dose, the flag indicating if the event occurred before or after vaccination (AE.AESTRTPT) will be used to complete the date. If ‘after study intervention’ is selected, the imputed start date will match the vaccine dose given during that year. If ‘before vaccination’ is selected, the imputed date will be one day before the vaccine dose given during that year.
- Adverse event end dates with missing day: the imputed end date will be the last day of the month or the study conclusion date whichever comes first.
- Adverse event end dates with missing day and month: the imputed end date will be the last day of the year (31st of December) or the study conclusion date whichever comes first.

Incomplete ARI onset/end dates will follow the rules analogous to above.

Incomplete concomitant medication/vaccination start/end dates will follow the rules analogous to above with CM.CMENRTPT status “BEFORE” or “ONGOING” status considered.

